F. Sample Size Estimation and Accrual

The endpoint of this pilot trial will be an immunological endpoint, i.e., the immune response rate at 6 months. Based on published results from a randomized trial using sipuleucel-T only in this population, in which proliferative T-cell responses specific for PAP were detected in 15 of 55 (27.3%) patients after immunization [7], and results from a phase I trial with this DNA vaccine only in which PAP-specific cytolytic T-cell responses were amplified after immunization in 7 out of 12 (58%) evaluable patients [23], it is anticipated that the immune response rate in the sipuleucel-T alone arm (Arm 1) will be 25% and that the addition of the pTVG-HP vaccine (Arm 2) will boost the response rate to at least 75%. An increase of 50% in the immune response rate will be considered as a clinically important difference. The following table shows the required sample sizes (per arm) to detect various differences in the immune response rates between the two arms with 80% power at the one-sided 5% significance level. These calculations are based on the stratified Mantel-Haenszel test with exact p-values.

Table 12.1 *Required sample sizes (per arm) to detect various differences in the immune response rates between the two arms with 80% power at the two-sided 5% significance level*

Immune Response Rate Arm 1 (sipuleucel-T alone arm)	Immune Response Rate: Arm 2 (sipuleucel-T + pTVG-HP vaccine arm)			
	70%	75%	80%	85%
15%	12	10	9	9
20%	15	12	10	9
25%	18	14	12	10
30%	23	18	15	12

A sample size of 14 patients per arm is proposed for this trial. This sample size is sufficient to detect an anticipated difference in the immune response rate of at least 50% (i.e., $\geq 75\%$ in Arm 2 vs. 25% in Arm 1) with adequate power ($\geq 80\%$) at the one-sided 5% significance level. The following table shows the attainable power levels to detect various differences in the immune response rates between arms at the one-sided 5% significance level, assuming a sample size of 28 evaluable (for immune response) patients.

Table 12.2: *Attainable power levels to detect various differences in the immune response rates between the two arms at the one-sided 5% significance level, assuming a sample size of 14 evaluable patients per arm*

	Immune Response Rate: Arm 2 (sipuleucel-T + pTVG-HP vaccine arm)			
Immune Response Rate Arm 1 (sipuleucel-T alone arm)	70%	75%	80%	85%
15%	85%	91%	96%	98%
20%	76%	85%	91%	96%
25%	65%	80%	84%	91%
30%	53%	65%	76%	85%

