A difference in the immune response rate of 55% between the two arms will be detected with at least 84% power. Analogously, a difference in the efficacy response rate of only 40% between the two arms will be detected with 53% power at the one-sided 5% significance level. In order to account for unevaluable patients, 30 eligible patients (15 per arm) will be accrued and randomized. Based on past experience with this patient population treated at our institution, we anticipate that the proposed total number of 30 patients will be accrued within 18 months. Each patient will be followed for at least 12 months.

G. Statistical Analysis Plan

G.1. General

This section outlines the statistical analysis strategy and procedures for the study. If after the study has begun changes are made to primary and/or key secondary objectives, or the statistical methods related to those objectives, then the protocol will be amended.

Summary tabulations will be presented that will display the number of observations, mean, standard deviation, median, range, minimum, and maximum for continuous variables and the number and percent per category for ordinal and categorical data. All endpoints of this study will be presented graphically where possible using boxplots and histograms for continuous variables and (stacked) bar charts for categorical variables. Data analysis will be performed using SAS[®] (SAS Institute Inc., Cary, North Carolina) version 9.2 or greater.

There are many comparisons made between the two trial arms for multiple measurements, both clinical and laboratory. However, since this a pilot study, no adjustment will be made for

multiple comparisons. Except for the primary immunological endpoint, where the comparison between arms will be conducted at the one-sided 0.05 significance level, all other comparisons will be made using a two-sided test at a significance level of 0.05 without adjustment for multiplicity.

G.2. Baseline Comparability

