PSA values will be summarized using standard descriptive statistics for each defined assessment time point (baseline, 3, 6, 9, and 12 months) in terms of number of observations, means, standard deviations, medians and ranges, stratified by study arm. Percentage changes from baseline to the 3, 6, 9, and 12 months assessment will be calculated. Changes within each arm will be evaluated using a paired t-test or nonparametric Wilcoxon Signed Rank test, if the percentage changes are not normally distributed. Analysis of variance, which will include study arm and baseline predicted survival (< 18 months vs. \geq 18 months) will be used to compare percentage changes in PSA values between study arms. If the percentage changes are not normally distributed and if a normality-improving data transformation is unavailable, then the stratified, nonparametric Wilcoxon rank-sum tests will replace the planned ANOVA. Changes in PSA levels will be presented graphically using waterfall plots.

PSA response rates (CR / PR) will be summarized in tabular format and compared between study arms using the Cochran-Mantel-Haenszel test, stratified by baseline estimated survival (< 18 months vs. \geq 18 months).

PSA doubling time for each patient is estimated as: $PSADT = \log(2)/b$, where b is the OLS estimator of slope parameter of the linear regression model $\log(PSA) = \alpha + \beta * \text{month} + \epsilon$. This method may result in negative PSA doubling time estimates. For analysis purposes, negative PSA doubling time estimates will be replaced by fixed positive PSA doubling time values (e.g., by the largest observed positive PSA doubling time value). Serum PSA doubling time will be summarized for each study arm by standard descriptive statistics in terms of means, standard deviations, medians and ranges. Percentage changes between pre-treatment and post-treatment PSA doubling times will be computed. Changes between pre- and post-treatment serum PSA doubling time within each arm will be assessed using a paired t-test and/or non-parametric Wilcoxon Signed Rank test. A two-sample t-test or non-parametric Wilcoxon Rank Sum test will be used to compare the changes in PSA doubling time from the pre- to the post-treatment assessments between study arms.

G.5. Correlative Analyses

G.5.1. Analysis for evaluating effects of treatment on the number of circulating tumor cells as determined by PSA ELISPOT

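### PSA doubling time is tested on a reciprocal scale with negatives replaced; the permitted t-test can lose much power that a log-PSA slope test would keep

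*Combined protocol and SAP*

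**What the plan says.** Section 12.G.4.4 fits a least-squares line of log PSA on month for each patient and takes the doubling time as log(2) divided by the slope b. Section 12.C.2.5 defines it the same way, once before and once after treatment. The plan concedes a difficulty: "This method may result in negative PSA doubling time estimates". Its remedy is that "negative PSA doubling time estimates will be replaced by fixed positive PSA doubling time values", with the parenthesis "e.g., by the largest observed positive PSA doubling time value". The value is therefore left open, and the pool from which a maximum would be taken (arm, period) is not stated.

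Doubling times are summarised by means, SDs, medians and ranges, and percentage changes are computed. Within an arm, the pre-to-post change "will be assessed using a paired t-test and/or non-parametric Wilcoxon Signed Rank test". Between arms, "A two-sample t-test or non-parametric Wilcoxon Rank Sum test will be used to compare the changes in PSA doubling time". For percentage change in PSA, the same section gives a normality rule for choosing the test and includes the predicted-survival stratum. It gives neither for doubling time. The slope b is never itself compared. Section 12.G.1 sets the level: "all other comparisons will be made using a two-sided test at a significance level of 0.05 without adjustment for multiplicity".

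**The concern.** The function log(2)/b is discontinuous at zero. Two patients with almost the same flat PSA course get doubling times at opposite extremes, and every falling PSA becomes whatever value is substituted. Means, SDs, percentage changes and t-tests are then governed by the few patients with slopes close to zero. The slope carries the same information, is defined for every sign and needs no replacement.

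At stake is the ability of a small trial to show an effect on PSA kinetics, which is a stated secondary objective. The choice between t-test and rank test, which matters a good deal here, is also left until the data are seen in an open-label study.

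**Working it through.** The plan states no power, effect size or SD for doubling time, so there is no figure to reproduce. The check is arithmetic on the scale, then simulation.

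**Inputs from the documents**
- Sample size, Section 12.F: "A sample size of 14 patients per arm is proposed for this trial", and "30 eligible patients (15 per arm) will be accrued and randomized".
- Two-sided 0.05 (Section 12.G.1) and doubling time = log(2)/b (Section 12.G.4.4).
- At least three pre-treatment PSA values over at least 12 weeks (Section 5.A, item 6), placed at -3, -1.5 and 0 months.
- Post-treatment values at the calendar visits, placed at 0, 1.4, 2.8, 5.5, 8.3 and 11 months.
- Proportional effect: doubling time doubled, as in the response definition in Section 10.C.

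**Assumptions not in the documents**
- Baseline doubling time about 3 or 6.5 months. The latter is the pre-treatment median quoted in Section 2.D for the earlier stage D0 trial, a different population.
- Residual SD of log PSA 0.03 to 0.15.
- Between-patient SD of the true slope change 0.05 to 0.10 per month (additive effect) or 0.5 on the log scale (proportional effect).
- Additive effects of 0.061 to 0.136 per month, chosen to give the slope t-test about 80% power.
- Negatives replaced by the largest positive value over both arms and periods.

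**Step 1: the scale.** log(2)/0.005 = 0.693/0.005 = 139 months, while a slope of -0.005 gives -139. If the flattest rising slope were 0.02, the largest value would be 0.693/0.02 = 35 months. With 3 of 15 patients replaced, moving the substitute from 35 to 139 moves the arm mean by 3 × (139 - 35)/15 = 21 months.

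**Step 2: power.** 14 per arm, 3,000 trials per row, so the Monte Carlo standard error is at most about 0.9 points (√(0.25/3000)). Entries are percentages, t-test / Wilcoxon; loss is the slope figure minus the doubling-time figure.

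| Scenario | Negative post-slopes, control / vaccine | Doubling-time change | Slope change | Loss |
|---|---|---|---|---|
| Additive, 6.5 months | 7 / 35 | 52.6 / 69.0 | 79.0 / 75.4 | 26.4 / 6.4 |
| Additive, 6.5 months, slopes 0.05 lower in both arms after treatment | 21 / 58 | 57.5 / 63.9 | 80.4 / 77.0 | 22.9 / 13.1 |
| Additive, 3 months | 4 / 23 | 49.1 / 71.2 | 79.8 / 75.8 | 30.7 / 4.6 |
| Additive, 3 months, low noise | 1 / 5 | 28.4 / 66.6 | 80.7 / 76.8 | 52.3 / 10.2 |
| Doubled, 3 months, noise 0.10 | 0 / 0 | 49.6 / 74.7 | 70.8 / 71.7 | 21.2 / -3.0 |
| Doubled, 6.5 months, noise 0.10 | 0 / 1 | 22.0 / 52.5 | 57.3 / 53.9 | 35.3 / 1.4 |
| Doubled, 3 months, noise 0.03 | 0 / 0 | 74.0 / 86.3 | 76.3 / 80.8 | 2.3 / -5.5 |

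At 15 per arm the pattern is the same.

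**Step 3: the cause.** Among the additive rows, the t-test loss is largest where only 1% and 5% of post-treatment slopes are negative. Leaving negatives unreplaced is far worse: in the additive rows, power is 2 to 9% (t-test) and 6 to 51% (Wilcoxon). Keeping the replacement but testing the change in log doubling time restores the t-test to 63 to 71% in those rows. The long tail of 1/b does most of the damage.

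**Step 4: the between-arm analysis proposed below.** A separate set of runs (14 per arm, 2,000 trials, log-SD of pre-slope 0.5, stratum omitted) gave power for doubling-time t / doubling-time Wilcoxon / ANCOVA of post-slope on arm and pre-slope:
- Additive: 36/50/66, 50/56/72 and 27/36/57 (6.5 months); 38/57/69 (3 months). ANCOVA gains 12 to 21 points over Wilcoxon.
- Doubled, 6.5 months, noise 0.10, 0.15, 0.03: 23/49/67, 14/32/60, 73/85/81.
- Doubled, 3 months, noise 0.10, 0.15, 0.03: 58/78/77, 36/65/74, 82/90/84. Over the six doubled scenarios, the difference from Wilcoxon runs from -6 to +28 points.

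These differences mix scale with covariate adjustment, so they are not like for like.

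**Step 5: no effect.** Rejection was 2 to 4% for the doubling-time t-test and about 5% for the slope tests (4.9 to 5.4% for ANCOVA).

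**The case against.** The strongest reply is that the plan already allows a rank test. Any large substitute places falling PSAs among the longest doubling times, and Wilcoxon against Wilcoxon the slope gains little. That stands: a reader might infer that the planned analysis loses much power whichever test is used, and the documents do not support this, because the large loss belongs to the t-test option alone. What remains is that nothing commits the plan to the rank test.

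A reader might also infer that the largest observed value is the rule, or that replacement is the culprit. The text gives that value only as an example, and Step 3 shows that replacement repairs more than it harms.

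The assumed effects are large. The earlier trial's medians, 6.5 and 8.5 months, correspond to slopes of 0.107 and 0.082, a change of about 0.025 per month. In runs with 15 per arm, an effect of 0.04 and noise SD 0.2, every test had only 8 to 19% power. With noise 0.1 the slope tests reached 53 to 58% against 43% for the Wilcoxon test on doubling time, which is better but still low.

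Finally, PSA declines are also examined through percentage changes, waterfall plots and response rates, and the trial is a pilot sized on immune response. Both points stand and bear on priority.

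**Conclusion.** The concern holds in a limited form. Testing change in doubling time lets a few near-flat slopes drive means, SDs and t-tests. The between-arm t-test loses roughly 20 to 50 points of power if the effect on slope is additive and about 2 to 35 if it is proportional. For the Wilcoxon test the like-for-like loss is about 5 to 13 points if additive; if proportional, it runs from about 1 point lost to 6 gained. These sizes rest on assumed slope variability, noise and effects. The discontinuity, the open replacement value and the absent rule for choosing the test do not rest on assumptions.

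It would be wrong to infer a risk of false positive claims, since rejection under no effect stays at or below about 5%. This is a secondary endpoint with no power statement, so the priority is minor.

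**What to change.** In Section 12.G.4.4, make the log-PSA slope b the tested quantity:
- Within arm: a paired test of post-treatment minus pre-treatment slope.
- Between arms: ANCOVA of post-treatment slope on arm, pre-treatment slope and predicted-survival stratum (below 18 months, 18 months or more).
- Doubling times: descriptive only, as medians, with non-positive slopes shown as 'not doubling' and no replacement.

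The cost is a few sentences; the regression output is the same and no new data are needed. There are two small downsides. A slope is less familiar to clinical readers, which the descriptive medians address. When noise is low and the effect is proportional, the rank test on doubling time can be slightly more powerful, by up to about 6 points in these runs.

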C.2.4. PSA Response

PSA complete response will be defined a decrease in PSA to <0.2 ng/mL. The decrease must be confirmed with PSA measurement a minimum of four weeks later (confirmed PSA CR). PSA partial response will be defined as reduction of at least 50% in baseline PSA.

C.2.5. PSA Doubling Time

PSA doubling time (PSADT) will be defined as the time it takes for the PSA value to double. PSADT will be calculated for each patient pre-treatment and post-treatment. The pre-treatment PSADT will be calculated from all available values obtained within 3-6 months prior to study enrollment, up to and including the baseline value. The post-treatment PSADT will be calculated from all PSA values obtained beginning with the PSA value at day 1 and continuing until the end-of study value. The pre-treatment and post-treatment PSADT will be calculated for each patient as the log 2 divided by the slope of the log PSA line, based on the linear regression model of log (PSA value) on time.

C.2.6. Evaluable for Immune Response

All patients who complete sipuleucel-T treatment at weeks 0, 2, and 4, and who have an immune response assessment at month 6 will be evaluable for immune response.

C.2.7. Analysis Populations

The ITT population consists of all patients who are randomized. The per-protocol population is defined as all patients who have been treated according to protocol, i.e., all inclusion/exclusion criteria are satisfied, and adequate treatment compliance of sipuleucel-T treatment and vaccine (pTVG-HP) is achieved.

D. Study Design

The study is designed as a randomized, two-arm, open-label, single institution pilot trial. Study arms will be defined as follows:

Arm 1: sipuleucel-T – administered intravenously (i.v.) per standard of care biweekly, weeks 0, 2, and 4.

Arm 2: sipuleucel-T – administered intravenously (i.v.) per standard of care biweekly, weeks 0, 2, and 4
 pTVG-HP (100 µg) with rhGM-CSF (208 µg) administered intradermally (i.d.) biweekly 4 times, then every 3 months to complete a 1-year treatment period (i.e. weeks 6, 8, 10, 12, then months 6, 9)

Eligible subjects will be randomly assigned in 1:1 fashion to either Arm 1 or Arm 2.

E. Randomization and Stratification

Eligible patients will be randomized to the two study arms with an allocation ratio of 1:1. The randomization will be based on permuted blocks of size 2-4, stratified by estimated survival (< 18 months, ≥ 18 months) using the Halabi nomogram [50].

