All measurements (variables) collected at baseline will be summarized and compared between study arms. These include demographic variables, lab parameters (CBC and platelets, creatinine, alk phos, SGOT, total bilirubin, amylase, LDH, serum testosterone and PSA and PAP) and medical history information. Comparisons between study arms of baseline variables on a continuous scale will be performed using a two-sample t-test and/or nonparametric Wilcoxon Rank Sum test. Comparisons between study arms of baseline variables on a categorical scale will be performed using Fisher's exact test.

G.3. Analysis of the Primary Immunological Endpoint: Immune Response Rate

Immune responses, obtained at 6 months, will be summarized in tabular format. Ninety-five percent confidence intervals for the proportions of patients with an immune response will be constructed for each study arm. The comparison of immune response rates between study arms will be performed using the Cochran-Mantel-Haenszel test, stratified by estimated survival (< 18 months, \geq 18 months) using the Halabi nomogram [50]. Due to the small sample size, exact p-values will be computed using Zelen's exact test for equal odds ratios for stratified 2 X 2 tables.

As a secondary analysis, "durable" immune responses will be determined by the presence of immune responses at one or more of the 3, 9, and 12 month time points evaluated after randomization. Immune responses determined at the 3, 9 and 12 month time points will be summarized in tabular format and compared between study arms using the Cochran-Mantel-Haenszel test, stratified by estimated survival (< 18 months, \geq 18 months) using the Halabi nomogram [50]. Furthermore, a generalized linear mixed effects model for binomial data with a logit link function will be employed to evaluate the longitudinal effects of immune responses measured at the 3-month intervals.

G.4. Analysis of Secondary and Exploratory Clinical and Immunological Endpoints

G.4.1. Analysis of 12-month Progression-Free Survival Rate

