The 12-month progression-free survival rate will be estimated for each arm using the Kaplan-Meier method. The 12-month progression-free survival rate, along with the corresponding two-sided 95% confidence intervals, will be reported for each arm. In order to evaluate the 12-month progression-free rate as a function of baseline time point (pretreatment or 3-months post treatment), the analysis will be conducted using two different baseline values: (1) Date of randomization, and (2) 3-months disease assessment.

G.4.2. Analysis of Progression-Free Survival

Progression-free survival will be estimated for each arm using the Kaplan-Meier method. The median progression-free survival, along with the corresponding two-sided 95% confidence intervals, will be reported for each arm. The comparison of progression-free survival between study arms will be performed using the stratified (by estimated survival at baseline, < 18 months vs. \geq 18 months) log-rank test. In order to evaluate progression-free rate as a function of baseline time point (pretreatment or 3-months post treatment, the analysis will be conducted using two different baseline values: (1) Date of randomization, and (2) 3-months disease assessment.

G.4.3. Analysis of Overall Survival

Overall survival will be estimated for each arm using the Kaplan-Meier method. The median overall survival, along with the corresponding two-sided 95% confidence intervals, will be reported for each arm. The comparison of overall survival between study arms will be performed using the stratified log-rank test.

G.4.4. Analysis of Changes in PSA Values, PSA Kinetics and PSA Doubling Time

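### The between-arm test of PSA doubling time leaves out the randomization stratum that the other arm-comparison tests use, so it is conservative if that stratum predicts the change

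*Combined protocol and SAP*

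**What the plan says.** Section 12.E sets the design. Allocation is 1:1, and "The randomization will be based on permuted blocks of size 2-4, stratified by estimated survival", with two strata: predicted survival below 18 months, or 18 months and above. Section 12.F gives the size: "30 eligible patients (15 per arm) will be accrued and randomized". Section 12.G.1 sets the level for everything except the primary endpoint: "all other comparisons will be made using a two-sided test at a significance level of 0.05 without adjustment for multiplicity".

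The planned between-arm outcome tests are as follows:

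- Immune response at 6 months (12.G.3): "performed using the Cochran-Mantel-Haenszel test, stratified by estimated survival". The same test is planned at 3, 9 and 12 months.
- Progression-free survival (12.G.4.2): "performed using the stratified (by estimated survival at baseline", by log-rank test.
- Overall survival (12.G.4.3): "The comparison of overall survival between study arms will be performed using the stratified log-rank test".
- Percentage change in PSA (12.G.4.4): analysis of variance with arm and predicted survival, with a stratified Wilcoxon rank-sum test as fallback.
- PSA response (12.G.4.4): Cochran-Mantel-Haenszel test, stratified by predicted survival.
- Circulating tumor cells (12.G.5.1): stratified Wilcoxon rank-sum test.
- Change in PSA doubling time (12.G.4.4): "A two-sample t-test or non-parametric Wilcoxon Rank Sum test will be used to compare the changes in PSA doubling time". No stratum is named, no reason is given, and nothing elsewhere in the document adds it.

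**The concern.** Permuted blocks of 2 to 4 within each stratum keep the two arms nearly balanced on predicted survival. Any difference between strata in the change in doubling time therefore contributes little to the arm difference. A plain two-sample test does not use this and leaves the between-stratum variation in its error term. The t-test then reports too large a standard error, and both the t-test and the rank-sum test reject less often than the stated 5% when there is no effect. The cost is lost power in a trial of 30 patients.

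The plan is also inconsistent with itself: within one subsection, PSA change and PSA response are analysed by stratum and PSA doubling time is not.

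**Working it through.** The plan states no standard deviation, effect size or power for PSA doubling time, so it has no figure of its own to reproduce. The check asks how far an unstratified test departs from its nominal level under the stated design.

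**Inputs from the documents.** 30 patients, 15 per arm (12.F); 1:1 permuted blocks of 2 to 4 within two strata (12.E); two-sided 0.05 (12.G.1).

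**Assumptions.** R², the share of variance in the change in doubling time that the stratum explains, is varied from 0 to 0.5. The strata are taken as equal in size, with a 30/70 split as a second case.

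**Standard error.** Let σ² be the variance of the change within an arm. With balanced strata, the true variance of the arm difference is (2/15)·σ²·(1 − R²). The unstratified t-test estimates (2/15)·σ². The reported standard error is therefore too large by a factor of 1/√(1 − R²).

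**Error rate and power, normal approximation.** Take an effect with non-centrality 2.80 against the unstratified standard error (80% nominal power, since 2.80 − 1.96 = 0.84).

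- Real two-sided error rate = 2·(1 − Φ(1.96/√(1 − R²)))
- Power, unstratified = Φ(0.84/√(1 − R²))
- Power, stratified = Φ(2.80/√(1 − R²) − 1.96)

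| R² | SE factor | Real error rate | Power, unstratified | Power, stratified |
|---|---|---|---|---|
| 0.10 | 1.054 | 3.9% | 81% | 84% |
| 0.20 | 1.118 | 2.8% | 83% | 88% |
| 0.30 | 1.195 | 1.9% | 84% | 92% |

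For R² = 0.20, √0.80 = 0.894. Then 1.96/0.894 = 2.19, which gives 2.8%; Φ(0.84/0.894) = Φ(0.94) = 83%; and Φ(2.80/0.894 − 1.96) = Φ(1.17) = 88%.

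**Simulation of the stated design.** Normal outcomes, 30 patients, blocks of 2 or 4, equal strata. Power is for a difference of 1 SD, whose non-centrality is 1/√(2/15) = 2.74, close to the 2.80 above. Each power cell gives unstratified / stratified.

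| R² | SE ratio | t-test error rate | Wilcoxon error rate | Power: t-test / ANOVA with stratum | Power: Wilcoxon / stratified Wilcoxon |
|---|---|---|---|---|---|
| 0 | 1.00 | 0.053 | 0.049 | 75% / 75% | 72% / 72% |
| 0.05 | 1.03 | 0.042 | not run | 76% / 78% | not run |
| 0.10 | 1.05 | 0.035 | 0.037 | 75% / 79% | 73% / 77% |
| 0.20 | 1.11 | 0.031 | 0.031 | 77% / 84% | 73% / 80% |
| 0.30 | 1.20 | 0.021 | 0.022 | 78% / 88% | 76% / 87% |
| 0.50 | 1.40 | 0.009 | 0.006 | 81% / 96% | 75% / 95% |

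With the stratum included, the error rate was between 0.046 and 0.056 at every R² tried. The t-test results at a 30/70 split were similar. At R² = 0 the unstratified interval was 0.997 times the width of the stratified one, so including a useless stratum costs almost nothing.

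**The case against.** The strongest reply is that nothing here is invalid. An unstratified test after stratified randomization is unbiased and does not inflate the error rate, and PSA doubling time is one secondary endpoint of a pilot that makes no power claim for it. That stands, and it is why the point is minor.

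The size is also unanchored. The stratum predicts survival; it has to predict a within-patient change in doubling time, and no figure for that is given. At R² = 0.05 the loss is only about 3% in interval width. This stands too, and the R² values are hypothetical.

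The outcome is also less well behaved than a normal variable. It is log 2 divided by a slope, and negative values are to be replaced, for example by the largest observed value. Under one set of assumed slopes (10 PSA values per patient, about 14% negative post-treatment slopes), a stratum explaining 10%, 20% or 30% of the variance in slope change explained only about 7%, 10% or 14% of the variance in doubling-time change, where about 3% is expected by chance. The t-test's error rate was then about 4.9%, 4.2% or 3.8%, and the rank-sum test's about 3.9%, 3.5% or 2.9%. So a sizeable stratum effect on slope may cost the t-test little. This is broadly consistent with the tables, which define R² on the doubling-time change itself.

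Three smaller points also stand:

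- The plan promises no confidence interval for the arm difference, so the overstated standard error is the one inside the t-test. For the rank-sum test the harm is a conservative p-value.
- The mixed model for immune response over time and the logistic models in 12.G.5 do not name the stratum either. They are longitudinal or association models, so the contrast with the planned arm-comparison tests remains.
- The overall survival and circulating tumor cell sections say the test is stratified without naming the factor. Predicted survival is the only stratification factor in the design.

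**Conclusion.** The point holds. PSA doubling time is the one planned arm-comparison outcome test that omits the randomization stratum, and the omission is unexplained. The consequence is conservative, with no bias and no excess false positives. If the stratum explains 10% to 30% of the variance in the change (assumed), the t-test's standard error is overstated by 5% to 20%, the real error rate falls to between 3.9% and 1.9%, and 3 to 8 points of power are lost in the normal approximation. The loss shrinks towards zero as the stratum explains less. Because stratifying costs practically nothing even then, this is a worthwhile minor improvement in efficiency and consistency, and not a threat to the trial's conclusions.

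**What to change.** In 12.G.4.4, replace the sentence on the between-arm comparison of doubling-time changes. State that the changes will be compared with a linear model containing study arm and predicted-survival stratum, or with the Wilcoxon rank-sum test stratified by predicted survival. The stratified rank-sum test is the natural choice if the changes are heavy-tailed or tied after negative values are replaced. Both methods already stand in that subsection for PSA change. The cost is one sentence in the plan, with no new data and no change to sample size. The edit does not settle how to choose between the parametric and rank-based test, or which value replaces a negative doubling time; those are separate matters.
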